5.3 Sample Storage, Tracking and Disposition

Samples will be ordered in CRIS and tracked through a Clinical Trial Data Management system. Should a CRIS screen not be available, the CRIS downtime procedures will be followed. Samples will not be sent outside the National Institutes for Health (NIH) without appropriate approvals and/or agreements, if required.

All samples will be barcoded, with data entered and stored in the secure databases. These databases create a unique barcode ID for every sample and sample box, which cannot be traced back to patients without database access. The data recorded for each sample includes the patient ID, name, trial name/protocol number, time drawn, cycle time point, dose, material type, as well as box and freezer location. Patient demographics associated with the clinical center patient number are provided in the system. For each sample, there are notes associated with the processing method (delay in sample processing, storage conditions on the ward, etc.).

Barcoded samples are stored in barcoded boxes in a locked freezer at either -20 or -80°C according to stability requirements.

Access to stored clinical samples is restricted. Samples will be stored until requested by a researcher named on the protocol. All requests are monitored and tracked in database. All researchers are required to sign a form stating that the samples are only to be used for research purposes associated with this trial (as per the IRB approved protocol) and that any unused samples must be returned. It is the responsibility of the NCI Principal Investigator to ensure that the samples requested are being used in a manner consistent with IRB approval.

5.3.2 Protocol Completion/Sample Destruction

All specimens obtained in the protocol are used as defined in the protocol. Any specimens that are remaining at the completion of the protocol will be stored in the conditions described in sections above. The study will remain open so long as sample or data analysis continues. Samples from consenting subjects will be stored until they are no longer of scientific value or if a subject withdraws consent for their continued use, at which time they will be destroyed. The PI will record any loss or unanticipated destruction of samples as a deviation. Reports will be made per the requirements of section [7.2](#).

If the patient withdraws consent the participant's data will be excluded from future distributions, but data that have already been distributed for approved research use will not be able to be retrieved.

6 DATA COLLECTION AND EVALUATION

6.1 Data Collection

The PI will be responsible for overseeing entry of data into a 21 CFR Part 11-compliant data capture system provided by the NCI CCR and ensuring data accuracy, consistency and timeliness. The principal investigator, associate investigators/research nurses and/or a contracted data manager will assist with the data management efforts. Primary and final analyzed data will have identifiers so that research data can be attributed to an individual human subject participant.

All adverse events, including clinically significant abnormal findings on laboratory evaluations, regardless of severity, will be followed until return to baseline or stabilization of event.

Document AEs from the first study intervention, day 1 of cycle 1 through 90 days after the study agent (s) was/were last administered. Beyond 90 days after the last intervention, only adverse events which are serious and related to the study intervention need to be recorded.

An abnormal laboratory value will be recorded in the database as an AE only if the laboratory abnormality is characterized by any of the following:

- Results in discontinuation from the study
- Is associated with clinical signs or symptoms
- Requires treatment or any other therapeutic intervention
- Is associated with death or another serious adverse event, including hospitalization
- Is judged by the Investigator to be of significant clinical impact

If any abnormal laboratory result is considered clinically significant, the investigator will provide details about the action taken with respect to the test drug and about the patient's outcome.

Information on all concomitant medications, administered blood products, as well as interventions occurring during the study must be recorded on the patient's eCRF.

End of study procedures: Data will be stored according to HHS, FDA, and NIH Intramural Records Retention Schedule regulations as applicable.

Loss or destruction of data: Should we become aware that a major breach in our plan to protect subject confidentiality and trial data has occurred, this will be reported expeditiously per requirements in section [7.2.1](#).

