⁶ EKG must be performed at screening and on Day 1 of every cycle. Echocardiogram must be completed at screening, C2D1, and every 3 cycles thereafter (i.e. C5D1, C8D1, etc.) and as clinically indicated. Troponin I test and cardiology consult only if clinically indicated.

⁷ HIV, Hepatitis B and C serology. If screening serology results indicate potential HBV or HCV infection, viral load will be tested before starting investigational agents. TB testing will be performed only if clinically indicated.

⁸ Biochemical Profile: electrolytes, BUN, creatinine, AST, ALT, total and direct bilirubin, calcium, phosphorus, albumin, magnesium.

⁹ Pregnancy test for female participants of childbearing potential (serum or urine; if urine is positive it must be confirmed with serum test

Abbreviated Title: Trametinib and HCQ in BTC

Version Date: 04/06/2022

¹⁰ CT scan of chest, abdomen and pelvis (or MRI of chest, abdomen and pelvis if clinically indicated) every 8 (+/-1) weeks after start of study therapy. If patient taken off treatment for reason other than progression, CT scans will continue until progression or 5 months have passed since the start of study therapy whatever comes earlier. MRI of brain can be done at screening if clinically indicated.

¹¹ Mandatory tumor biopsies will be performed at baseline and any day during week 3 of cycle 2. If patient disease progresses before this, post-treatment biopsy might be performed per PI discretion at the time of progression.

¹² On Day 1 of cycles 1-4, then every 12 weeks until PD

¹³ +/- 1 week

¹⁴ After Safety Follow Up visit, subjects will be followed for adverse events by phone call or e-mail at 60 (+/- 14 days) and 90 (+/- 14 days) days. After that every 6 (\pm 1) months by phone call or e-mail for survival. If patient is taken off treatment for reason other than disease progression before 5 months have passed since the start of study therapy, we will continue to invite patient every 8 (+/-1) weeks for imaging studies until disease progression or 5 months have passed since the start of study therapy whatever comes earlier. Outside scans are acceptable.

¹⁵ If patients are not willing to come to the NIH Clinical Center, they may be followed by phone call or e-mail.

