4.1 Prohibited Therapy

The following medications are not permitted to be taken concurrently with study therapy.

- Any other anti-cancer systemic therapy.
- Other investigational agents.
- Any live vaccines (Inactivated vaccines are allowed).
- The following QT prolonging agents: mesoridazine, thioridazine, pimozide, terfenadine, cisapride, sparfloxacin, saquinavir, ziprasidone, dronedarone, piperaquine, amisulpride (Other agents with the possibility of QT prolongation should be used with caution).
- Non-steroid anti-inflammatory medications (i.e. naproxen, ibuprofen, piroxicam, diclofenac, meloxicam).
- Anti-platelet agents (i.e. clopidogrel, prasugrel, dipyridamole).
- Serotonin reuptake inhibitors (SSRIs) should be used with caution.
- Tamoxifen.

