In addition to evaluation of the proportion of patients that are progression-free at 5 months, the progression-free survival for patients will also be analyzed via a Kaplan-Meier curve. This curve will be compared informally to other published results in similar patients. As well, the overall response rate will be reported, and the overall survival will be reported using a Kaplan-Meier curve. It is anticipated that up to 10 patients per year will be able to enroll onto this protocol. Thus, it is expected that accrual of up to 17 total patients can be completed in approximately 2 years. In order to allow for a small number of unevaluable patients and screen failures, the accrual ceiling will be set at 30 patients.

To evaluate the response rate, proportion of patients obtaining CR and PR per RECIST 1.1 criteria of all evaluable patients will be analyzed.

To address safety, tolerability and feasibility of trametinib in combination with hydroxychloroquine, adverse events will be tabulated by grade according to CTCAE and analyzed and reported descriptively. The fraction of patients who experience a response will be reported along with confidence intervals.

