10.3 Population for Analysis

Any patient who receives at least one dose of both agents will be included in the efficacy evaluations.

Any patients who receive at least one dose of either agent will be included in the safety evaluations.

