10.4.4 Safety analysis

The safety of the treatment will be monitored, and any toxicities identified will be reported by type and grade.

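### The adverse event tabulation has no cut or split at the start of another anti-cancer therapy, so events from the 90 days after the last dose may include toxicity of a following regimen

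*Combined protocol and SAP*

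**What the plan says.** **Collection.** Section 6.1 has AEs documented from "day 1 of cycle 1 through 90 days after the study agent (s) was/were last administered". It then narrows the scope: "Beyond 90 days after the last intervention, only adverse events which are serious and related to the study intervention need to be recorded". Within the 90 days there is no condition on relationship, and section 8.2 confirms that AEs are documented whether or not they are related. Laboratory abnormalities count as AEs only if they meet the criteria listed in 6.1. Footnote 14 of the Study Calendar (3.4) adds active follow-up after the 28-day safety visit: "subjects will be followed for adverse events by phone call or e-mail at 60 (+/- 14 days) and 90 (+/- 14 days) days".

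**Tabulation.** Section 10.2 states that "adverse events will be tabulated by grade according to CTCAE and analyzed and reported descriptively". Sections 10.4.3 and 10.4.4 use slightly different words: "The safety of the treatment will be monitored, and any toxicities identified will be reported by type and grade". Section 10.3 defines who is counted ("Any patients who receive at least one dose of either agent will be included in the safety evaluations") but not over what event period.

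**Other therapy.** Section 4.1 lists other systemic anti-cancer therapy under the rule "The following medications are not permitted to be taken concurrently with study therapy". Under 3.6.1, starting a therapy that rules out further study treatment ends protocol therapy. It is not among the off-study criteria in 3.6.2.

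**The concern.** Safety and tolerability of the doublet is a secondary objective, and there is no control arm in which a background of later-line toxicity could be seen. A patient who progresses, stops both drugs and starts another regimen a few weeks later is still inside the AE window and still on study. Cytopenias, nausea, fatigue or liver abnormalities caused by that regimen would be recorded. Under the wording of 10.2 they would be counted in the same table as events that arose on trametinib plus HCQ. The direction of the error is known: it can only add events to the doublet's profile. With about 17 patients, each patient moves an incidence by 1/17 = 5.9 percentage points.

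**Working it through.** The plan gives no figure of its own on this point, so there is none to reproduce. The check is first textual, then a bound.

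**Text, taken in sequence**

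1. AE collection continues for 90 days after the last dose, whatever the relationship (6.1, 8.2).
2. Other anti-cancer therapy is barred only while study therapy is being taken (4.1), so it may start within those 90 days.
3. Starting it does not take the patient off study (3.6.2), so step 1 still applies.
4. AEs are tabulated by grade (10.2). No section defines a treatment-emergent period or splits events by attribution or by next therapy.
5. The calendar marks concomitant medications at screening, baseline and day 1 of each cycle, and in neither follow-up column.

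Steps 1 to 4 together place a following regimen's AEs in the doublet's table. Step 5 means the date needed to separate them is not tied to a follow-up contact.

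**How much of the AE window is off treatment**

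Inputs: 90 days (6.1); median PFS of 2.5 months (historical) and 5 months (target), and the exponential model (10.2); 30.44 days per month. Assumptions: treatment runs until the PFS event, and deaths within the 90 days are ignored.

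- Patient stopping at the historical median: 2.5 × 30.44 = 76.1 days; 90 / (76.1 + 90) = 0.54.
- Average, historical median: mean = 76.1 / ln 2 = 109.8 days; 90 / (109.8 + 90) = 0.45.
- Average, target median: 5 × 30.44 = 152.2 days; mean = 152.2 / ln 2 = 219.6 days; 90 / (219.6 + 90) = 0.29.

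Only part of that time could be spent on another therapy. If one began 14 days after the last dose, 90 − 14 = 76 days would overlap it; if after 28 days, 90 − 28 = 62. Fourteen days is the gap that section 2.1.2 requires after standard therapy, used here only as an indication of how soon a next therapy might start. For the patient stopping at the historical median these are 76 / 166.1 = 46% and 62 / 166.1 = 37% of the window.

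**Chance that at least one patient is affected (illustration)**

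The share q starting another therapy within 90 days, and the chance a that such a patient then has a recorded AE, are not in the documents. The ranges are assumed. With n = 17 (10.2):

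| q (assumed) | At least one starts: 1 − (1 − q)^17 | At least one has an AE: 1 − (1 − qa)^17, a = 0.5 to 0.8 |
|---|---|---|
| 10% | 83% | 58% to 76% |
| 20% | 98% | 83% to 95% |
| 50% | >99.9% | 99% to >99.9% |

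**The case against.** The strongest reply is that most of what is needed to separate the events is already to be collected. Section 6.1 requires other medicines and interventions given during the study to be entered on the eCRF, and patients in the 90-day follow-up are still on study. Section 8.2 asks for onset date, relationship and alternate etiology. This stands in part. A reader might infer that the data for a split would be missing, and the documents do not support that. What remains is that no next-therapy start date is named, the calendar's follow-up columns do not match 6.1, and 8.2 sits under a heading on device effects. Above all, no table uses these items.

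Second, the toxicities of the treatment in 10.4.3 and 10.4.4 can be read as attributed events. That reading is possible, but 10.2 speaks of adverse events without restriction, so the plan leaves two readings open.

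Third, this table is not the only evidence on safety. The run-in judges dose-limiting toxicities over 28 days, only if attributable to the combination, and is the only enrolment rule based on safety. That stands: no go/no-go decision, error rate or efficacy result depends on post-treatment AEs.

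Fourth, section 1.2.1 says there is no standard second-line option, which may make prompt further treatment less common. This also stands, and it is why the size cannot be stated.

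Finally, a reader might infer that the comparison with the triplet's safety table in 1.2.6.3 would be distorted. Section 10 plans no such comparison, and 1.2.6.3 does not give that trial's AE window, so nothing can be said about it.

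**Conclusion.** The concern holds as a gap in the analysis rule, not in data collection. As written, AEs with onset after the start of another anti-cancer therapy, but within 90 days of the last dose, fall into the doublet's safety table. That table may therefore include toxicity of a following regimen.

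The documents do not support saying that it will. The share of patients who start another therapy in the window is not given, and a patient who does so need not have a recordable AE. Nor are 54%, 45% and 29% the contaminated share of the table. They are shares of off-treatment time and bound the time on another therapy from above, provided treatment runs to progression. Deaths inside the 90 days would lower them; earlier stopping for toxicity would raise them. The illustration shows only that, with 17 patients, even an assumed 10% starting another therapy makes at least one such patient likely (83%).

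The consequence is limited to a descriptive secondary objective. The primary analysis, sample size and run-in rule are unaffected. The matter is still worth settling before the data are seen, because a choice of event period made afterwards would be open to question.

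**What to change.** Keep the 90-day collection unchanged, and make three changes.

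1. **Event period.** In 10.2 and 10.4.4, state that the main AE table covers events with onset from cycle 1 day 1 to the earlier of 90 days after the last dose and the start of another anti-cancer therapy. Tabulate later events separately.
2. **Attribution.** Show both tables for all events and for events attributed to the study drugs. This also settles what is meant by toxicities in 10.4.3 and 10.4.4. It keeps late study-drug events visible, which matters because section 1.2.6.2 notes that HCQ retinal changes may progress after the drug is stopped.
3. **Date of next therapy.** Align the calendar with 6.1 by recording the start date of any new anti-cancer therapy at the 28-day visit and the 60- and 90-day contacts.

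The cost is some protocol wording, one date field at contacts already planned and one more table. The downside is that a late study-drug event arising after a new therapy has started appears in the second table instead of the main one; the attribution display is there so that it is not lost. Sample size, alpha and power do not change.

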1.2.6.3 Toxicities of the combination of trametinib and HCQ

There is no data available in terms of this combination though there should have this information accessible in the near future since several trials involved with this combination is ongoing. However, there is safety data from the BAMM trial (NCT02257424), that is designed for patients with advanced BRAF mutant melanoma treated with dabrafenib, trametinib, and hydroxychloroquine. The doses of trametinib and hydroxychloroquine used in the BAMM trial is the exact same as we plan in our trial except that we are not planning BRAF inhibitor dabrafenib. Therefore, this precious data will provide important reference for our trial. From personal communication with [name] (Primary Investigator of BAMM trial, University of Pennsylvania), we summarize the safety profile from BAMM trial as showed in the following **Table 3**.

Table 3. Safety profile in the BAMM Study

Adverse Event	Dabrafenib + trametinib + HCQ (BAMM)	
	Grade 1-2	Grade 3
Chills	14 (56%)	1 (4%)
Diarrhea	13 (52%)	0
Fever	13 (52%)	1 (4%)
Nausea	12 (48%)	1 (4%)
Fatigue	11 (44%)	0
Headache	9 (36%)	0
Myalgia	9 (36%)	0
Rash	9 (36%)	3 (12%)
Anorexia	8 (32%)	0
Dry mouth	7 (28%)	0
Pruritus	7 (28%)	0
Arthralgia	6 (24%)	0
Abdominal pain	5 (20%)	0
Vomiting	5 (20%)	0
Constipation	4 (16%)	0
Dysgeusia	4 (16%)	0
Creatinine increased	3 (12%)	0
Dehydration	3 (12%)	2 (8%)
QTc prolonged	3 (12%)	1 (4%)
Increased alanine aminotransferase	1 (4%)	2 (8%)
Ejection fraction decreased	0	1 (4%)

With the triplet combination, the most common adverse effects are chills, diarrhea, fever, nausea, rash, and fatigue with grade 1-2. No grade 4 AEs are reported. This information indicates the less adverse effects we foresee with trametinib and hydroxychloroquine in our trial.

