3.3.2 Hydroxychloroquine

Table 4 Guidelines for hydroxychloroquine-related toxicities

Adverse Event	1 st Occurrence	2 nd Occurrence
Hematology Grade 4 neutropenia lasting \geq 7 consecutive days Grade 4 thrombocytopenia \geq 7 consecutive days Grade \geq 3 neutropenia with fever (temperature \geq 38.5 °C)	Hold HCQ and trametinib. Continue weekly hematologic monitoring. Once AE resolves to \leq Grade 1, restart study drugs, with HCQ at next lower dose level.	Discontinue HCQ and trametinib
Skin and subcutaneous tissue disorders Grade \geq 3 rash, hand-foot skin reaction or photosensitivity lasting $>$ 7 consecutive days despite skin toxicity treatment	See Table 5	Discontinue HCQ and trametinib
Eye disorders Grade 2 retinal events lasting $>$ 14 consecutive days confirmed by ophthalmologic examination Grade \geq 3 retinal events confirmed by ophthalmologic examination	Hold HCQ and trametinib. Monitor until AE resolves to Grade \leq 1. Patients should be referred for ophthalmologic exam. Restart study drugs, with HCQ at next lower dose level.	Discontinue HCQ and trametinib
Gastrointestinal Grade \geq 3 nausea or vomiting lasting \geq 7 days despite optimal anti-emetic therapy	Hold HCQ and trametinib. Monitor until AE resolves to Grade \leq 1. Restart study drugs, with HCQ at next lower dose level.	Discontinue HCQ and trametinib
Grade \geq 3 diarrhea lasting \geq 7 days despite optimal anti-diarrhea treatment	See Table 6	Discontinue HCQ and trametinib
Hepato-biliary Grade \geq 3 total bilirubin felt to be not related to progression of disease Grade \geq 3 ALT (isolated increases in AST without concomitant increases in ALT will not be considered dose-limiting because of the non-specific nature of AST) Grade 4 alkaline phosphatase lasting \geq 7 consecutive days felt to be not related to progression of disease	Hold HCQ and trametinib. Monitor with weekly CMP until AE resolves to Grade \leq 1. Restart study drugs, with HCQ at next lower dose level.	Discontinue HCQ and trametinib
ECG QT Interval	Hold HCQ and trametinib. Monitor	Discontinue HCQ

Abbreviated Title: Trametinib and HCQ in BTC**Version Date: 04/06/2022**

Adverse Event	1 st Occurrence	2 nd Occurrence
QTcF interval \geq 501 ms on at least two separate ECGs	with ECG until AE resolves to Grade \leq 1. Restart study drugs, with HCQ at next lower dose level.	and trametinib

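### Section 6.1 admits laboratory abnormalities as adverse events only under five triggers that omit CTCAE grade and dose action, so asymptomatic graded laboratory toxicity may be undercounted

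*Combined protocol and SAP*

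**What the plan says.** Safety, tolerability and feasibility form the first secondary objective (1.1.2, 10.1.2). For this objective, section 10.2 states that "adverse events will be tabulated by grade according to CTCAE and analyzed and reported descriptively". Sections 10.4.3 and 10.4.4 add that observed toxicities will be classified by kind and grade. No section describes a worst-grade or shift table for laboratory data.

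Section 6.1 sets the rule for turning a laboratory result into an adverse event: "An abnormal laboratory value will be recorded in the database as an AE only if the laboratory abnormality is characterized by any of the following". The conditions are:

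- leaving the study because of it (in the protocol's words, "Results in discontinuation from the study");
- accompanying symptoms or signs;
- a need for therapy (in the protocol's words, "Requires treatment or any other therapeutic intervention");
- a link to a death or to some other SAE, admission to hospital among them;
- the investigator considers its clinical impact significant.

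Section 6.1 then asks the investigator to describe what was done with the study drug, but only for results already held to be clinically significant.

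Table 4 (3.3.2) works differently. Its adverse-event column includes ALT and bilirubin of Grade 3 or higher and creatinine of Grade 2 or higher. For the hepatobiliary entries the first-occurrence instruction begins "Hold HCQ and trametinib. Monitor with weekly CMP until AE resolves to Grade" 1 or lower, and treatment restarts with HCQ reduced. Section 3.1.1 likewise defines laboratory DLTs by grade or by a multiple of the upper limit of normal. Section 6.1 refers to neither.

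The Study Calendar (3.4) schedules blood counts and chemistry on Day 1 of each cycle, and weekly until the first restaging and every two weeks after that. Results from outside laboratories are accepted.

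**The concern.** The safety table can show only what the recording rule lets in. An asymptomatic rise in ALT that needs no treatment and no admission meets none of the first four triggers on a plain reading, whatever its grade, unless a dose hold counts as an intervention. It is then recorded only if the investigator judges it important. The same result can, under Table 4, interrupt both drugs and lower the HCQ dose.

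Two parts of one protocol thus give different answers to whether a graded laboratory result is an adverse event. In patients with hepatobiliary disease, liver tests are a central part of the tolerability question. If the table depends on case-by-case judgment, its laboratory rows cannot be read as incidence.

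**Working it through.** The plan states no figure on this point, so there is none to reproduce. The check compares the rules and then sizes what is exposed to them.

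**Rules side by side**

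| Laboratory event | 3.1.1 or Table 4 | 6.1, if asymptomatic and untreated |
|---|---|---|
| ALT Grade 3 or higher | Listed as adverse event; both drugs held, HCQ reduced | Only by judgment, or if a hold counts as an intervention |
| Bilirubin Grade 3 or higher, not from progression | Same | Same |
| Creatinine Grade 2 or higher | Listed as adverse event; action depends on cystatin C | Only by judgment, or if a hold follows and counts |
| Grade 1-2 ALT, AST, anemia or low albumin | No entry | Only by judgment |

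**Inputs**

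- N = 17, the full two-stage total (10.2). The safety set is everyone given a dose of either drug (10.3), so N could be 10 after a first-stage stop. It cannot exceed the ceiling of 30, which also allows for screen failures.
- Trametinib alone, METRIC (Table 2), all grades / Grade 3-4: AST 60/2%, low albumin 42/2%, ALT 39/3%, anemia 38/2%, alkaline phosphatase 24/2%.
- BAMM triplet (Table 3): Grade 3 ALT in 2 patients (8%), which implies 2/0.08 = 25 patients.
- Share of abnormalities that meet a trigger, c: not given in the documents. I let it run from 0 to 1.

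**Formulas.** Expected patients = N × p. Chance of at least one = 1 − (1 − p)^N, assuming independent patients.

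| Test (N = 17) | p | Expected | Chance of at least one |
|---|---|---|---|
| AST, albumin, anemia, alkaline phosphatase (each), Grade 3-4 | 2% | 17 × 0.02 = 0.34 | 1 − 0.98^17 = 29% |
| ALT, Grade 3-4, METRIC | 3% | 17 × 0.03 = 0.51 | 1 − 0.97^17 = 40% |
| ALT, Grade 3, BAMM | 8% | 17 × 0.08 = 1.36 | 1 − 0.92^17 = 76% |

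For ALT with N = 10 the chances are 26% (3%) and 57% (8%). With N = 30 they are 60% and 92%.

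**Split by grade.** The five all-grade rates sum to 2.03 and the five Grade 3-4 rates to 0.11. For 17 patients that is 17 × 2.03 = 34.5 patient-abnormalities, of which 17 × 0.11 = 1.9 are Grade 3-4 and 32.6 are Grade 1-2. The Grade 1-2 share is 1.92/2.03, about 95%.

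**Effect of capture.** Expected omissions = N × p × (1 − c). For Grade 3 ALT at 8% this is 1.36 at c = 0, 0.68 at c = 0.5 and 0 at c = 1. The documents do not narrow that range.

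**The case against.** The strongest reply is that the protocol already catches what matters. The fifth trigger is open-ended, and the third can be read to cover a dose hold. An investigator who stops both drugs for a Grade 3 ALT would hardly call it clinically unimportant, and Table 4 already labels it an adverse event. DLTs in the run-in are documented separately. The wording on toxicities in 10.4.3 and 10.4.4 would permit a laboratory table, and because the tests are scheduled throughout, one could be added at analysis. Safety is a descriptive secondary objective with no decision rule attached to this table. Leaving lymphopenia and isolated AST out of the DLTs is a deliberate choice.

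Much of this stands, and it rules out three stronger readings that a reader might take from 6.1:

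- *That undercounting is certain.* The third and fifth triggers can bring in held-dose events, so the text supports only that it may occur.
- *That the doublet has never been tried.* Section 1.2.6.3 says "There is no data available in terms of this combination", but 1.2.4.2 reports ten patients treated elsewhere and one at the NIH Clinical Center, and Table 3 gives triplet data with the same two drugs. The two sections should be reconciled.
- *That six to ten of 17 patients per test could vanish.* The all-grade rates give such counts (17 × 0.60 = 10.2 for AST), but they are almost wholly Grade 1-2, and the share recorded is unknown.

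What does not stand is that no gap remains. Permitting a laboratory table is not planning one. The run-in covers six patients for 28 days, and its DLT exceptions also set aside results that the investigator deems insignificant. Leaving a result out of dose decisions is no reason to leave it out of a toxicity table.

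**Conclusion.** The point holds as a cheap improvement to reporting. As written, 6.1 allows asymptomatic graded laboratory toxicity to be left out of the safety table at the investigator's discretion, and it is not aligned with 3.1.1 and Table 4. Omission is most likely for Grade 1-2 values. For Grade 3-4 it is a matter of judgment and involves few patients: about 0.3 to 0.5 of 17 per test at the Table 2 rates, and 1.4 of 17 for Grade 3 ALT at the BAMM rate. With counts this small, one case recorded or not changes the reported profile visibly.

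These sizes assume that rates from trametinib alone in melanoma, or from a triplet with dabrafenib, carry over to this doublet in biliary cancer. The documents cannot confirm that. They bound the number of patients exposed to the rule and do not estimate how many would be missed. Sample size, error rates and clinical rules are unaffected.

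**What to change.** 1. **In 10.4.4**, commit to a table of each patient's worst on-treatment CTCAE v5.0 grade per laboratory test, with shift from baseline, derived from all protocol laboratory values whether or not an adverse event was recorded. This captures the Grade 1-2 values, which wider triggers alone would mostly still miss. State which tests are covered: alkaline phosphatase is graded in 3.1.1 and Table 4 but is not named in the biochemical profile in 3.4.
2. **In 6.1**, reconcile the triggers with 3.1.1 and Table 4. Record as an adverse event any laboratory abnormality that led to a hold, reduction or stop of either drug, or that met a laboratory threshold for a DLT or in Table 4. This concerns recording only and leaves the dose rules as they are.

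The cost is one programmed table, a short addition to 6.1 and some extra data entry, including values from outside laboratories. The safety table will probably look less favorable, which the sponsor should expect.
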